2.2 OUTCOME MEASURES

The outcome measures are described in the protocol synopsis ([Appendix 1](#)).

2.3 DETERMINATION OF SAMPLE SIZE

The global study plans to enroll approximately 600 patients, including 480 patients with detectable *PIK3CA*-mutant tumors and 120 patients without detectable *PIK3CA*-mutant tumors (tumor status determined by the cobas[®] *PIK3CA* Mutation Test).

After the global enrollment closes, additional Chinese patients may continue to be recruited into the China extension cohort. A total of up to 150 patients with detectable *PIK3CA*-mutant tumors may be enrolled as part of the global study population and the China extension cohort combined (refer to the protocol for details).

The sample size of 480 patients with detectable *PIK3CA*-mutant tumors is determined on the basis of the power calculation for the PFS and the OS endpoints, whichever requires a larger sample size. In this case, the sample size is driven by OS.

Among the 480 patients with *PIK3CA*-mutant tumors, approximately 287 investigator-assessed PFS events will be required to detect a hazard ratio (HR) of 0.59 in PFS (3.1 months of improvement in median PFS) with 95% power at a two-sided significance level of 1%, assuming a median PFS of 4.5 months in the control arm ([Mauriac et al. 2009](#); [Johnston et al. 2013](#)). One interim efficacy analysis of investigator-assessed PFS will be conducted at 60% of PFS information (see [Section 4.8](#) for more details). The α -spending function is specified as Gamma ($\alpha = 16$), which allocates two-sided $\alpha = 1.7 \cdot 10^{-5}$ at the interim efficacy analysis of PFS, when 172 investigator-assessed PFS events have occurred. The minimal detectable difference for PFS HR at final PFS analysis is 0.72 (i.e., 39% improvement in median PFS from 4.5 months in the control arm compared with 6.2 months in the treatment arm), when 287 investigator-assessed PFS events have occurred.

With the aforementioned sample size of 480 patients with *PIK3CA*-mutant tumors, the OS analyses in this population will require 330 deaths to detect an HR of 0.7 with at least 80% power at a two-sided significance level of 5%. Timeline for the analyses of OS is detailed in [Section 2.4](#). OS will be tested only if both the investigator-assessed PFS and ORR have reached their respective significance levels.

The study plans to enroll 120 patients who do not have a detectable *PIK3CA*-mutant tumor, based on the cobas[®] *PIK3CA* Mutation Test, to estimate the clinical benefit in this population. For this group of patients, the focus is to estimate the benefit, and formal hypothesis testing will not occur. For example, If the observed HR in PFS is 1 (no evidence of benefit), the 90% CI will exclude a true HR <0.72 (i.e., > 1.8-month improvement in median PFS). These analyses are exploratory.

In total, approximately 400 patients will be treated with the combination of taselisib + fulvestrant in this study (320 patients with detectable *PIK3CA*-mutant tumors and 80 patients without detectable *PIK3CA*-mutant tumors), which will enable the Sponsor to better characterize any rare but clinically significant safety events (e.g., for an adverse event with 4% frequency, there is a 96% probability to observe • 10 patients with such an adverse event based on 400 patients treated with taselisib + fulvestrant) to help enable the development of effective toxicity prevention and management guidelines for patients treated with the combination of taselisib and fulvestrant.

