With the aforementioned sample size of 480 patients with *PIK3CA*-mutant tumors, the OS analyses in this population will require 330 deaths to detect a hazard ratio of 0.7 in OS (11.1 months of improvement in median OS) with 80% power at a two-sided significance level of 5%, assuming a median OS of 26 months in the control arm based on the OS of 26.4 months in patients treated with 500 mg fulvestrant in the CONFIRM study, which investigated 500 mg fulvestrant versus 250 mg fulvestrant in a similar patient population (Di Leo et al. 2014).

The study plans to enroll 120 patients who do not have a detectable *PIK3CA*-mutant tumor, on the basis of the result of the cobas *PIK3CA* mutation test, to evaluate the clinical benefit in this population. If the observed hazard ratio in investigator-assessed PFS is 1 (no benefit), approximately 111 investigator-assessed PFS events will be observed at the analysis, and the 90% confidence interval will exclude a true hazard ratio < 0.72 (i.e., > 1.8 -month improvement in median PFS).

In total, approximately 400 patients will be treated with the combination of taselisib + fulvestrant in this study (320 patients with *PIK3CA*-mutant tumors and 80 patients without detectable *PIK3CA*-mutant tumors), which will enable the Sponsor to better characterize any rare but clinically significant safety events (e.g., for an adverse event with 4% frequency, there is 96% probability to observe ≥ 10 patients with such adverse event on the basis of 400 taselisib + fulvestrant-treated patients) to help enable the development of effective toxicity prevention and management guidelines for patients treated with the combination of taselisib and fulvestrant.

Interim Analyses

The iDMC will convene to review cumulative safety data approximately every 6 months. Data on serious adverse events, death, and adverse events of special interest will be monitored by the iDMC approximately every 3 months.

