Until approximately the end of August 2018, tumor assessments will be conducted for all patients 8 weeks (± 5 days) from the date of randomization and then every 8 weeks (± 5 days) thereafter, regardless of dose delays or dose interruptions, until 4–6 weeks after investigator-assessed disease progression or until death, whichever occurs first. After approximately the end of August 2018, tumor assessments may be conducted per local standard of care.

Patients may *remain on* study treatment until disease progression (as assessed by the investigator), unmanageable toxicity, or study termination by the Sponsor. Patients who discontinue taselesib/placebo due to toxicity may continue on single-agent fulvestrant at the discretion of the investigator. Discontinuation of fulvestrant for adverse events is very rare. However, in the unlikely event that the patient discontinues fulvestrant and is able to continue on taselesib/placebo, the investigator should contact the Medical Monitor to discuss the benefit-risk assessment of continuing with single-agent taselesib/placebo. All patients who are discontinued from all study treatment will return for a study drug discontinuation visit within 28 days after the last dose of study treatment (see [Section 4.5.10](#) for additional details).

Until approximately the end of August 2018, patients who are discontinued from study treatment for reasons other than disease progression will be asked to continue to have

tumor assessments performed and to complete the PRO assessments approximately every 8 weeks (± 5 days) until disease progression.

Until approximately the end of August 2018, after study treatment discontinuation, patients will be followed for survival and subsequent anti-cancer therapies approximately every 3 months until death, loss to follow-up, withdrawal of consent, or study termination by the Sponsor.

Until approximately the end of August 2018, after experiencing disease progression, patients will also be asked to return to the clinic approximately 4–6 weeks (for tumor and PRO assessments) and 12 weeks (± 1 week] for PRO assessments), even if a patient initiates anti-cancer therapy subsequent to study drug discontinuation.

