6. STATISTICAL CONSIDERATIONS AND ANALYSIS PLAN

6.1 DETERMINATION OF SAMPLE SIZE

The global study plans to enroll approximately 600 patients, including 480 patients with detectable *PIK3CA*-mutant tumors, and 120 patients without detectable *PIK3CA*-mutant tumors (tumor status determined by the cobas *PIK3CA* mutation test).

After the global enrollment closes, additional Chinese patients may continue to be recruited into the China extension cohort. A total of up to 150 patients with detectable *PIK3CA*-mutant tumors may be enrolled as part of the global study population and the China extension cohort combined (see Section 6.10 for further details).

The sample size of 480 patients with *PIK3CA*-mutant tumors is determined on the basis of the power calculation for the PFS and the OS endpoints, whichever requires a larger sample size. In this case, the sample size is driven by OS.

In 480 patients with *PIK3CA*-mutant tumors, approximately 287 investigator-assessed PFS events will be required to detect a hazard ratio of 0.59 in PFS (3.1 months of

improvement in median PFS) with 95% power at the a two-sided significance level of 1%, assuming a median PFS of 4.5 months in the control arm (Mauriac et al. 2009; Johnston et al. 2013). One interim efficacy analysis of investigator-assessed PFS will be conducted at 60% of PFS information (see Section 6.9.1 for more details). The α -spending function specified as Gamma (-16), which allocates two-sided $\alpha = 1.7 \times 10^{-5}$ at the interim efficacy analysis of investigator-assessed PFS, when 172 investigator-assessed PFS events have occurred. The minimal detectable difference for investigator-assessed PFS hazard ratio at final PFS analysis is 0.72 (i.e., 39% improvement in median investigator-assessed PFS from 4.5 months in the control arm compared with 6.2 months in the treatment arm), when 287 investigator-assessed PFS events have occurred.

With the aforementioned sample size of 480 patients with *PIK3CA*-mutant tumors, the OS analyses in this population will require 330 deaths to detect an hazard ratio of 0.7 in OS (11.1 months of improvement in median OS) with 80% power at a two-sided significance level of 5%, assuming a median OS of 26 months in the control arm based on the OS of 26.4 months in patients treated with 500 mg fulvestrant in the CONFIRM study, which investigated 500 mg fulvestrant versus 250 mg fulvestrant in a similar patient population (Di Leo et al. 2014).

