6.4.2.2 Overall Survival

The analyses for OS will be conducted in all randomized patients with *PIK3CA*-mutant tumors as a secondary endpoint of the study and will be tested on the basis of a hierarchical testing procedure to preserve type I error. That is, the OS analysis will be tested only if both investigator-assessed PFS and ORR have reached their respective significance levels. The overall type I error for OS is preserved at two-sided 5%.

OS will be analyzed with patients grouped according to the treatment arm assigned at randomization. Data for patients who are alive at the time of the analysis data cutoff will be censored at the last date they were known to be alive. Data from patients without post-baseline information will be censored at the date of randomization.

The analyses will be conducted using the stratified two-sided log-rank test, and the results from the unstratified log-rank test will also be provided. The OS curve for each treatment arm will be estimated by the Kaplan-Meier methodology, and the HR and its 95% CI will be estimated by the Cox proportional-hazards models.

Three interim analyses and one final analysis for OS *were originally* planned in patients with *PIK3CA*-mutant tumors on the basis of the results from the cobas *PIK3CA* mutation test (see [Table 12](#) and [Table 13](#)). *As a result of the completion of the primary PFS analysis, the Sponsor has decided to limit the additional OS follow-up to one additional analysis. This additional OS analysis coincides with the originally planned second OS interim analysis.*

1. The first interim OS analysis will be conducted at the time when both investigator-assessed PFS and ORR have reached their respective significance levels, so it could occur at the time of the interim efficacy or the final efficacy analysis for investigator-assessed PFS.
2. The second OS analysis will be conducted approximately 10 months after the first interim analysis.

Table 12 Analyses for OS if the First Interim OS Analysis Occurs at the Time of the Interim Efficacy Analysis of Investigator-Assessed PFS

	Estimated Timing (Clinical Data Cutoff)	OS Events	Two-Sided p-Value Boundary	Rejection HR Boundary ^a	Percentage Information
First OS IA	~21 months after FPI	~63	0.001	0.44	19%
Second OS analysis	~10 months after first OS IA	~134	0.010	0.65	41%

IA=interim analysis; FPI=first patient in; HR=hazard ratio; OS=overall survival; PFS=progression-free survival.

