^a Assuming exponential distributions for the OS event time of the two treatment arms.

Table 13 Analyses for OS if the First Interim OS Analysis Occurs at the Time of the Final Efficacy Analysis of Investigator-Assessed PFS

	Estimated Timing (Clinical Data Cutoff)	OS Events	Two-Sided p-Value Boundary	Rejection HR Boundary ^a	Percentage Information
First OS IA	~29 months after FPI	~118	0.001	0.53	36%
Second OS analysis	~10 months after first OS IA	~188	0.010	0.67	57%

IA=interim analysis; FPI=first patient in; HR=hazard ratio; PFS=progression-free survival.

^a Assuming exponential distributions for the OS event time of the two treatment arms.

The stopping boundaries are computed using the generalized Haybittle-Peto boundaries with unequal p-values being used in the α -spending function and will be adjusted on the basis of the actual number of OS events observed at each interim OS analysis.

The timing of the analyses are based on an assumption of an annual loss-to-follow-up rate of 5%. The study team will be unblinded at the time when the iDMC recommends to stop the study and the Sponsor decides to stop the study, or at the time of the final PFS analysis if the study is not stopped early. Investigators and patients will remain blinded to individual patient-level treatment assignment until *approximately the end of August 2018, at which time unblinding is permitted at the discretion of the investigator or Sponsor.*

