4.4.2.2 Overall Survival

OS is defined as the time from randomization to death from any cause. The analysis for OS will be conducted only in all randomized patients with detectable *PIK3CA*-mutant tumors as a secondary endpoint of the study and will be tested based on a hierarchical testing procedure to preserve type I error. That is, the OS will be tested only if both investigator-assessed PFS and ORR have reached their respective significance levels. The overall type I error for OS is preserved at two-sided 5%.

OS will be analyzed with patients grouped according to the treatment arm assigned at randomization. Data from patients who are alive at the time of the analysis data cutoff will be censored at the last date they are known to be alive. Data from patients without post-baseline information will be censored at the date of randomization.

The analyses will be conducted using the stratified two-sided log-rank test, and the results from the unstratified log-rank test will also be provided. The OS curve for each treatment arm will be estimated by the Kaplan-Meier method, and the HR and its 95% CI will be estimated by Cox proportional hazards models.

Three interim analyses (time driven) and one final analysis (event driven) for OS are planned in patients with detectable *PIK3CA*-mutant tumors (see [Table 2](#) and [Table 3](#)):

- The first interim OS analysis will be conducted at the time when both investigator-assessed PFS and ORR have reached their respective significance levels, so it could occur at the time of the interim efficacy or the final efficacy analysis for investigator-assessed PFS.
- The second interim analysis will be conducted approximately 10 months after the first interim analysis.
- The third interim analysis will be conducted approximately 8 months after the second interim analysis.
- The final analysis will be conducted after approximately 330 deaths are observed (approximately 77 months after FPI).

Table 2 Interim Analyses for Overall Survival if the First Interim Overall Survival Analysis Occurs at the Time of the Interim Efficacy Analysis of Investigator-Assessed Progression-Free Survival

	Estimated Timing (Clinical Data Cutoff)	OS Events	Two-Sided p-Value Boundary	Rejection HR Boundary ^a	Percentage Information
First OS IA	~21 months after FPI	~63	0.001	0.44	19%
Second OS IA	~10 months after first OS IA	~134	0.010	0.65	41%
Third OS IA	~8 months after second OS IA	~188	0.045	0.75	57%

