OS FA	~77 months after FPI	~330	0.007	0.74	100%

FA=final analysis; FPI=first patient in; HR=hazard ratio; IA=interim analysis; OS=overall survival; PFS=progression-free survival.

^a Assuming exponential distributions for the OS event time of the two treatment arms.

Table 3 Interim Analyses for Overall Survival if the First Interim Overall Survival Analysis Occurs at the Time of the Final Efficacy Analysis of Investigator-Assessed Progression-Free Survival

	Estimated Timing (Clinical Data Cutoff)	OS Events	Two-Sided p-Value Boundary	Rejection HR Boundary ^a	Percentage Information
First OS IA	~29 months after FPI	~118	0.001	0.53	36%
Second OS IA	~10 months after first OS IA	~188	0.010	0.67	57%
Third OS IA	~8 months after second OS IA	~232	0.045	0.76	70%
OS FA	~77 months after FPI	~330	0.013	0.75	100%

FA=final analysis; FPI=first patient in; HR=hazard ratio; IA=interim analysis; OS=overall survival; PFS=progression-free survival.

^a Assuming exponential distributions for the OS event time of the two treatment arms.

The stopping boundaries are computed using the generalized Haybittle-Peto boundaries with unequal p-values being used in the α -spending function and will be adjusted on the basis of the actual number of OS events observed at each interim OS analysis.

The timing of the analyses are based on an assumption of an annual loss-to-follow-up rate of 5%. The study team will be unblinded at the time when the iDMC recommends to stop the study and the Sponsor decides to stop the study or at the time of the final PFS analysis if the study is not stopped early. Investigators and patients will remain blinded to individual patient-level treatment assignment until the final analysis of OS.

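### The stated 80% OS power is not met under SAP Table 2 (about 74%), and the two OS looks that protocol version 4 keeps have only about 40% power at HR 0.7

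*Combined protocol and SAP*

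**What the plan says.** **SAP.** Section 2.3 attaches "330 deaths to detect an HR of 0.7 with at least 80% power at a two-sided significance level of 5" percent to the OS analyses, with no condition. Section 4.4.2.2 then gives two alternative schemes: "The stopping boundaries are computed using the generalized Haybittle-Peto boundaries with unequal p-values". Each has three interim looks and a final, and overall OS type I error is held at two-sided 5%.

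- Table 2 (first OS look at the PFS interim): about 63, 134, 188 and 330 deaths, with p-value boundaries 0.001, 0.010, 0.045 and 0.007.
- Table 3 (first OS look at the final PFS analysis): about 118, 188, 232 and 330 deaths, with boundaries 0.001, 0.010, 0.045 and 0.013.

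On the last look the SAP says: "The final analysis will be conducted after approximately 330 deaths are observed (approximately 77 months after FPI"). SAP section 1 says the SAP overrides the protocol's statistical section.

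**Protocol version 4.** Section 6.1 still says the OS analyses will require "330 deaths to detect an hazard ratio of 0.7 in OS (11.1 months of improvement in median OS) with 80% power" at two-sided 5%, and the synopsis says the same. Section 6.4.2.2 says "the Sponsor has decided to limit the additional OS follow-up to one additional analysis". Tables 12 and 13 accordingly stop at the second look; in Table 13 the looks are at about 118 deaths (0.001) and 188 deaths (0.010). Section 3.1 limits survival follow-up: "Until approximately the end of August 2018, after study treatment discontinuation, patients will be followed for survival and subsequent anti-cancer therapies".

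**The concern.** OS drives the sample size of 480 and stands third in the testing hierarchy, after PFS and ORR, so its stated power is a design figure that readers will rely on. Two things looked wrong.

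1. The four-look schemes spend most of the 5% before the final analysis. A power figure that suits one scheme need not suit the other, and SAP 2.3 makes no distinction.
2. Version 4 removes the two most generous opportunities to reject, the 0.045 look and the 330-death final, and leaves the 330-death, 80% sentence in place.

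A reader who sees 80% in both documents would take a non-significant OS result at about 188 deaths as evidence against HR 0.7. If true power there is well under one half, that reading is wrong.

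**Working it through.** **Inputs.** HR 0.70 and 330 deaths (SAP 2.3, protocol 6.1). Randomization 2:1 (SAP section 1). Deaths and two-sided p-value boundaries from SAP Tables 2 and 3 and protocol Tables 12 and 13.

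**Method.** With 2:1 allocation, information is I = deaths × (1/3)(2/3) = deaths × 2/9. The log-rank Z at each look has mean −ln(0.70)·√I = 0.3567·√I and unit variance; the correlation between looks i<j is √(I_i/I_j). Reject at look k if Z exceeds the normal quantile for p/2: 3.291 (0.001), 2.576 (0.010), 2.005 (0.045), 2.697 (0.007), 2.484 (0.013).

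**Step 1: single 5% look.** I = 330 × 2/9 = 73.33, so the mean of Z is 3.054 and power is Φ(3.054 − 1.960) = 86.3%. This exceeds 80%, but neither document plans a single look.

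**Step 2: the SAP's four looks, HR 0.70.**

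| Scheme | Deaths | Mean Z | Cumulative power |
|---|---|---|---|
| SAP Table 2 | 63 / 134 / 188 / 330 | 1.335 / 1.946 / 2.305 / 3.054 | 2.5 / 26.7 / 62.3 / **73.9%** |
| SAP Table 3 | 118 / 188 / 232 / 330 | 1.826 / 2.305 / 2.561 / 3.054 | 7.2 / 39.6 / 71.4 / **79.3%** |

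Table 3 reproduces the plan's 80% within a point. Table 2 falls about 6 points short.

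**Step 3: type I error.** At HR 1 both schemes give 5.0% two-sided, so the p-values have been read as intended. In Table 2 the 0.045 look at 188 deaths uses 3.72 percentage points of the 5, and the final look adds only 0.24. That is where the power goes.

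**Step 4: alternatives for Table 2.**

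- Log-rank simulation: 76.4%. This used 12,000 trials of 480 patients at 2:1, exponential OS with control median 26 months, 28-month accrual and 5% annual loss. The linear shape of the 12-month ramp is an assumption. The standard error is about 0.4 points.
- The printed HR boundaries (0.44, 0.65, 0.75, 0.74) as the rejection rule: 78.3%, but with type I error 7.2%.
- Information as for 1:1 allocation: 79.2%, but the trial is 2:1.

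None reaches 80%. For Table 3 the simulation gives about 82%, and its printed HR boundaries give 80.0%.

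**Step 5: which timing applies.** The amendment rationale reports primary PFS p=0.0037. That meets the final boundary of 0.01 and not the interim boundary of 1.7×10⁻⁵, so only Table 3 / Table 13 timing can apply.

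**Step 6: the looks that version 4 keeps, HR 0.70.**

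| Looks kept | Power | Simulation | Two-sided alpha used |
|---|---|---|---|
| 118 and 188 deaths (Table 13) | 7.2 + 32.4 = **39.6%** | about 44% | 1.04% |
| 63 and 134 deaths (Table 12) | 2.5 + 24.2 = **26.7%** | about 31% | 1.06% |

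At 118 and 188 deaths, 80% power needs a true HR of about 0.59 (79.9% at 0.59).

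**The case against.** The strongest reply is that the Table 2 shortfall could not arise in this trial: PFS did not cross at its interim, and on the timing that remains the SAP's four-look plan delivers roughly its stated 80%. That is correct. The Table 2 point is a fault in a prospective statement, not in the trial's conduct.

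The SAP sentence might also be read as a fixed-design calculation, for which 86.3% makes it true. That reading is hard to sustain: the sentence speaks of OS analyses in the plural, and the next one sends the reader to section 2.4, which describes the four looks.

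The truncation is openly disclosed. Table 13 prints 57% information and a rejection HR of 0.67 against a design HR of 0.70, from which a careful reader could infer power below one half. The SAP also predates version 4, which explains why it lags. Both facts stand, but neither corrects the 80% sentence that version 4 itself still carries in section 6.1 and the synopsis.

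The printed HR boundaries in SAP Table 2 largely match 1:1 information (0.436, 0.641, 0.746, 0.743) rather than 2:1 (0.415, 0.624, 0.733, 0.730). This may explain how the 80% arose. It is a separate inconsistency, shared by protocol Table 12, and does not rescue the stated power.

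Finally, OS is tested only if ORR is also significant, boundaries will be adjusted to actual deaths, and the HR with its 95% CI will be reported anyway. These limit the practical consequence, and realised power will differ somewhat from the planned figure.

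**Conclusion.** The concern holds. SAP 2.3's unqualified claim is wrong for Table 2, where power is 74% (74–79% across the methods tried, always below 80%), and approximately right for Table 3 (79–82%). The larger matter is protocol version 4: the two looks it keeps at about 118 and 188 deaths have about 40% power at HR 0.70 (44% by simulation), half of what sections 6.1 and the synopsis state. The plan that remains would miss that effect more often than detect it.

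These figures assume 2:1 allocation, proportional hazards, the planned death counts and the printed p-value boundaries, and they are conditional on OS being tested at all. Type I error is not in question. The point should be corrected, but it does not undermine the trial.

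**What to change.** Leave the OS p-value boundaries unchanged, because the sponsor is already unblinded. State which plan governs, then:

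- If the SAP's four looks stand, restate OS power in SAP 2.3 by scheme: about 74% for Table 2 and about 80% for Table 3.
- If protocol version 4 governs, remove the third-look and final rows from SAP Tables 2 and 3. Replace the 330-death, 80% sentence in SAP 2.3, protocol 6.1 and the synopsis with the power of the two remaining looks: about 40% at 118 and 188 deaths (about 27% at 63 and 134).

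Give the method beside the figure, since simulation puts it a few points higher. The cost is wording and table rows only: sample size, follow-up and conduct do not change. The stated OS power becomes visibly less favourable.
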